## ***Secondary Endpoints***

### **1. Time to progression.**

This endpoint reflects the time between randomization and radiological progression as defined by the amendments of the Response Evaluation Criteria in Solid Tumors (RECIST) (16).

**A. Complete Response** is defined as the disappearance of any intratumoral arterial enhancement in all target lesions.

- B. Partial Response** is at least a 30% decrease in the sum of diameters of viable (contrast enhancement in the arterial phase) target lesions, taking as reference the baseline sum of the diameters of target lesions.
- C. Progressive Disease** is an increase of at least 20% in the sum diameters of viable (enhancing) target lesions, taking as reference the smallest sum of the diameters of viable (enhancing) target lesions recorded since the treatment started. Or the appearance of one or more new lesions.

A newly detected hepatic nodule will be classified as HCC- and will be declared as evidence of progression- when its longest diameter is at least 10 mm and the nodule shows the typical vascular pattern of HCC on dynamic imaging. Lesions larger than 10 mm that do not show a typical vascular pattern can be diagnosed as HCC by evidence of at least 1 cm interval growth in subsequent scans.

- D. Stable Disease** is any cases that do not qualify for either partial response or progression disease.

MRI or CT-scan of the abdomen will be used to determine the targeted lesions for treatment and its baseline measurements. Target lesions will be measured using a single linear summation of the large diameter of the tumor. The average of two measurements by two independent radiologists will be considered for baseline and follow up assessment.

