## **Proton Beam Radiotherapy**

Proton beam radiotherapy has physical properties that target the actual tumor mass and spare large portions of nearby normal tissues. Phase I and II trials demonstrated the safety of this treatment modality in decompensated patients with cirrhosis with HCC. Few trials in Southeast Asia and the United States demonstrated that proton beam could be an effective treatment that may improve survival and control tumor progression. Tokuyue et al. treated 79 patients who had HCC with proton beam radiotherapy (12). A median total dose of 72 Cobalt gray equivalents in 16 fractions was delivered. At 5 years, local tumor control and survival rates were 89% and 27% respectively. Kawashima et al. used the same fractionation scheme in 30 patients with HCC with an indocyanine green retention rate at 15 minutes. Complete disappearance of tumors occurred in 24 patients (80%). The 2-year local regression-free rate in that study was 96%, and the 1-year and 3-year survival rates were 77% and 62% respectively (13). Eight patients developed hepatic insufficiency, which presented as ascites, elevated transaminase levels, and/or asterixis from 1 to 4 months after therapy (13). Bush et al., in a phase II trial where 34 patients with HCC completed 15 sessions of total 63 cobalt Gray equivalents, 75% local tumor control rate and overall survival rate of 55%. Six patients underwent liver transplantation 6 to 18 months after proton therapy. In 2 patients, there was no evidence of tumor pathology, demonstrating that proton therapy can eradicate HCC (14). A complete pathologic response was also observed by Merle et al (15). Risks involved in proton treatment include internal bleeding, radiation hepatitis (elevation in liver enzymes), worsening liver function (elevation in

bilirubin and INR) and perforation of the surrounding solid organ such as small bowel and stomach.

Proton beam radiotherapy has been associated with some of the best outcomes in HCC patients; however, further studies are needed to compare proton to other treatments.

In this randomized trial we wish to compare head-to-head the efficacy of proton beam radiotherapy versus TACE in treating patients with unresectable HCC.

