## ***Follow Up***

Patients with HCC usually require either CT scan or MRI of the abdomen to be performed routinely every three months to monitor tumor progression. Patients undergoing any locoregional treatment usually require a CT scan or MRI of the abdomen to be performed 4-6 weeks after the treatment and then every three months. Follow up imaging will be the same modality used at baseline (CT or MRI). Patients are usually evaluated in the liver clinic 4 weeks after treatment and then every three months. Subjects receiving proton therapy will also be followed in radiation medicine clinic by their treating radiation oncologist every 3 months for the first year then every 6 months. Participants in this study will be followed according to this protocol. No radiological testing will be ordered for the purpose of the study as the recommended assessments follow the current standard of care. Patients will be followed for research purposes until death or transplant, or until which time the study investigators determine the study is complete.

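### Target-lesion progression is a 20% rise over the smallest viable sum with no minimum absolute increase, so the rule fails at a sum of 0 mm and is fragile at small residuals

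*Combined protocol and SAP*

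**What the plan says.** Under Secondary Endpoints, Time to progression, item C, progressive disease in target lesions is "an increase of at least 20% in the sum diameters of viable (enhancing) target lesions"; any new lesion also counts. The baseline for that percentage is not the pre-treatment scan but the lowest value reached on study: "taking as reference the smallest sum of the diameters of viable (enhancing) target lesions recorded since the treatment started". Item A defines complete response as "disappearance of any intratumoral arterial enhancement in all target lesions".

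The same section gives absolute sizes only for nodules outside the target set. A newly detected nodule counts as HCC, and so as progression, "when its longest diameter is at least 10 mm and the nodule shows the typical vascular pattern of HCC on dynamic imaging"; an atypical one needs 1 cm of interval growth. For target lesions there is no minimum increase, no minimum size of re-appearing enhancement, no confirmation scan and no rule for a reference sum of zero. None appears elsewhere in the document.

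Two provisions limit reading noise. Time to progression states: "The average of two measurements by two independent radiologists will be considered for baseline and follow up assessment". Follow Up keeps the imaging modality the same as at baseline and schedules scans "4-6 weeks after the treatment and then every three months".

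**The concern.** A purely relative threshold shrinks with its reference. When little or no viable tumour is left, the increase that counts as progression becomes smaller than the error of the measurement, and at zero the percentage has no meaning. Two readers could then date progression differently in the same patient while both follow the protocol.

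This matters for the comparison because patients with deep responses are the ones with small reference sums. If small sums are also read with relatively more error, time to progression penalises depth of response.

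Small sums are plausible here. Exclusion Criteria admit lesions from 2 cm, so a 10 mm residual is only a 50% fall for the smallest eligible tumour. The Proton Beam Radiotherapy section cites one series with complete disappearance in 24 of 30 patients (80%). That is not this trial's population or its definition of complete response, but a zero reference cannot be assumed to be rare.

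**Working it through.** The plan derives no figure for time to progression, so there is nothing to reproduce. The check takes the stated rule and asks how it behaves when nothing has changed.

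**1. Increase needed (no assumptions).** Required increase = 0.20 × smallest sum.

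| Smallest viable sum | Increase that counts |
|---|---|
| 0 mm | undefined, or any enhancement |
| 5 mm | 1 mm |
| 10 mm | 2 mm |
| 20 mm | 4 mm |
| 30 mm | 6 mm |
| 50 mm | 10 mm |

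A 10 mm sum is a fall of 1 − 10/20 = 50% from the smallest eligible lesion, 1 − 10/65 = 85% from the largest eligible solitary lesion, and 1 − 10/80 = 87.5% from the largest total diameter (Appendix 1).

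**2. One comparison, unchanged residual.** Let the true sum be μ and the single-reader SD be s (assumed; the protocol gives none). With independent errors, the two-reader mean has variance s²/2. If Y is the current reading and R the reference reading, Y − 1.2R has mean −0.2μ and variance (1 + 1.44)s²/2 = 1.22s². Hence

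P(false progression) = Φ(−0.2μ / (s√1.22)).

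For μ = 10 and s = 2: Φ(−2/2.209) = Φ(−0.905) = 18%. For μ = 50 and s = 3: Φ(−10/3.314) = Φ(−3.02) = 0.1%.

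**3. Five scans.** The first post-treatment scan plus four later ones covers about the first year of the Follow Up schedule. The reference is the running minimum, and the true residual is held constant. Simulated probability of at least one false progression:

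| Single-reader SD | 10 mm, 20% rule | 10 mm, 20% and 5 mm | 50 mm, 20% rule |
|---|---|---|---|
| 0.5 mm | 0.1% | 0% | 0% |
| 1 mm | 23% | 0% | 0% |
| 1.5 mm | 54% | 0.4% | 0% |
| 2 mm | 72% | 5% | 0% |
| 3 mm | 86% | 29% | 1% |

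Two-reader averaging is already in these figures. The 5 mm minimum binds only below 25 mm, because 0.20 × 25 = 5.

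**4. Does the error fall unequally?** The formula in step 2 depends only on μ/s. With s fixed in millimetres, risk rises as the residual shrinks. With s proportional to μ, it is constant: simulated false progression is 23%, 54% and 72% at reader CVs of 10%, 15% and 20%, the same at 10, 30 and 50 mm. A gradient therefore needs some fixed-millimetre component.

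**5. Illustration with fixed error (assumed response mix).** Let no patient truly progress, with SD 2 mm, and false progression of 72% at 10 mm and 2.8% at 30 mm. An arm with half its patients at each size has 0.5 × 72 + 0.5 × 2.8 = 37%; an arm with 20% at 10 mm and 80% at 30 mm has 0.2 × 72 + 0.8 × 2.8 = 17%. With the 5 mm minimum (5% and 2.8%) these become 3.9% and 3.2%.

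**6. Delay from a 5 mm minimum (noise-free growth from 10 mm).** At 20% per scan: 12, 14.4, 17.3 mm. The 20% rule is met at scan 1 and the 15 mm needed with the minimum at scan 3, two scans later. At 10% per scan: 11, 12.1, 13.3, 14.6, 16.1 mm, so scan 2 against scan 5, three scans (about 9 months) later. From 5 mm the delays are three and six scans.

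**The case against.** The strongest reply is that the link to depth of response rests on how reading error scales. The documents give neither an SD nor a model, and purely proportional error removes the gradient (step 4). Under that model a 5 mm minimum would itself create an imbalance: at a 15% CV, false progression falls to 0.4% at 10 mm but stays at 54% at 50 mm. This stands. It makes the differential effect conditional and is a reason to report both rules.

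A reader might infer that the rule can reverse the treatment comparison. The documents do not support that. They give no response rates by arm and do not say which arm will respond more deeply, and true progression among poorer responders works in the other direction. Step 5 shows a mechanism under an assumed mix, not a reversal.

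A reader might also infer that the 10 mm rule for new nodules shows the section to be inconsistent, or that re-enhancement after complete response is usually false. Neither follows. The new-nodule rule decides whether an undiagnosed nodule is HCC, whereas target lesions are already diagnosed. Re-enhancement may be genuine recurrence, and the simulation gives no false-progression rate for a zero reference.

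Reader averaging and a constant modality do reduce noise, but neither sets a minimum. The section cites published response criteria that are not available here; the rule it writes out has no minimum.

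**Conclusion.** The concern holds as a defect in a stated rule. Two parts need no assumptions: after complete response the criterion is undefined or met by any trace of enhancement, and at residuals of 10 mm or less a rise of 2 mm or less is progression.

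The frequency of false progression does rest on assumptions: a constant true residual, five scans, independent reader errors and an assumed SD. At 10 mm it runs from 0.1% (SD 0.5 mm) to 86% (SD 3 mm), so reader precision decides whether the problem is negligible or dominant. Larger false-progression rates in the arm with deeper responses follow only if error has a fixed-millimetre component. The size of any bias cannot be computed from the documents.

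Time to progression is a secondary endpoint. Overall survival and the sample size are untouched. The change should be made, but the primary result does not depend on it.

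**What to change.** Before outcomes are read, amend item C so that target-lesion progression requires an increase of at least 20% **and** at least 5 mm over the smallest viable sum. Add an explicit minimum size of re-appearing arterial enhancement for use when the smallest sum is 0 mm. The 10 mm that the section uses for new nodules is one option, though that figure was written for a different purpose. Report the present 20%-only rule as a sensitivity analysis.

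The 5 mm figure is a choice, not a value taken from the documents. It does not remove the problem if readers are imprecise (29% at SD 3 mm).

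No extra scans or readers are needed. The cost is later detection of true regrowth in small residuals: about two to three scans from 10 mm at the growth rates in step 6, and longer from smaller residuals. The delay applies to both arms but affects more patients where more residuals are small, which is a further reason to show both analyses.

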## **2. Downstaging**

This endpoint will be applied to subjects in whom their tumor burden exceed Milan criteria but meet San Francisco criteria (Appendix 1). The direct measurement of the longest diameter of the viable tumor will be compared pre-and-post treatment. Usually, patients with San Francisco criteria will not be qualified for MELD score exception upgrade on UNOS waiting list unless their tumor burden is down-staged to Milan criteria using one of the locoregional treatments. Measuring this endpoint will help in comparing the efficacy of proton versus TACE in downstaging tumor in patients who meet San Francisco criteria.

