## **Data and Statistics**

Data will be evaluated according to intent to treat analysis. One- and two-year survival will be compared between two groups using competing risk analysis. This analysis will provide an estimate of HCC-related death in the presence of alternate yet plausible outcomes such as death from liver failure or liver transplantation. It is also a better technique in illustrating differential rates of competing outcomes in patients waiting for liver transplantation. This analysis will limit the effects of confounding factors such as death from liver disease. Secondary end points will be compared using Student's *t*-test for quantitative data and chi-squared ( $\chi^2$ ) test or Fisher's exact test for qualitative data. Demographics and standard of care laboratory data between groups will be compared. Logistic regression will be used to determine independent factors affecting survival.

The study is designed and powered to show at least 15% difference in mortality between two groups. Group size is calculated by assuming that patients in the TACE group will have at least 15% improvement in 2-year survival compared to the proton beam group. With 110 patients in each group the study has 80% power to detect a 15% difference in the mortality between two groups. We are not expecting any significant drop out because both treatments are considered crucial for patients' survival; and also based on our experience in treating these patients for many years at LLUMC. The level of significance is 0.05 (2-sided) for all statistical tests. The Statistical Package for the Social Sciences (SPSS 16.0 for window; SPSS, Inc., Chicago, Illinois) was used for all statistical analyses.

We will conduct an interim analysis after randomizing 40 patients in each group. This analysis will determine if there is any early significant difference in survival between two groups. The interim report will be submitted to the Institutional Review Board.

Data will be collected anonymously and subjects will be identified using a numerical code. The code will be stored at the PI and Co-PI office. The study database will be maintained and stored in the department of radiation medicine. Only PI, CO-PI and research coordinators will have access to the data.

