## **Appendix 1**

## **Tumor Classification**

### **Milan Criteria**

Solitary lesion  $\leq$  5 cm or  $\leq$  3 lesions, none of  $>$  3 cm

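### The downstaging comparison has only unadjusted tests; adjusting for baseline viable diameter and solitary/multiple disease is a free improvement whose gain depends on an outcome scale the plan has not fixed

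*Combined protocol and SAP*

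**What the plan says.** All references are to the combined protocol and SAP.

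- **Population** (Secondary Endpoints, 2. Downstaging): "This endpoint will be applied to subjects in whom their tumor burden exceed Milan criteria but meet San Francisco criteria". The number of such patients is not given.
- **Measure** (same section): "The direct measurement of the longest diameter of the viable tumor will be compared pre-and-post treatment". The clinical purpose is transplant listing, since these patients do not qualify "unless their tumor burden is down-staged to Milan criteria using one of the locoregional treatments". The section does not say whether the outcome is post-treatment diameter, change, percent change or Milan reached yes/no, nor at which scan it is read.
- **Test** (Data and Statistics): "Secondary end points will be compared using Student's" *t*-test for quantitative data, and the chi-squared "test or Fisher's exact test for qualitative data". No covariate or stratum is named.
- **The only regression** (Data and Statistics): "Logistic regression will be used to determine independent factors affecting survival". It does not cover downstaging.
- **Baseline data** (Secondary Endpoints, 1. Time to progression): lesion diameters at baseline and follow-up are the mean of two independent radiologists' readings. Lesion number must be known to apply the San Francisco criteria at entry.
- **Randomisation** (Methods): 1:1, with no stratification factor named.

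**The concern.** Both sets of limits in Appendix 1 allow up to three lesions, so only lesion size puts a patient beyond Milan but within San Francisco. The subset mixes solitary tumours of over 5 to 6.5 cm with multiple disease whose largest lesion is over 3 to 4.5 cm. A solitary 5.1 cm tumour needs 0.1 cm of shrinkage to meet Milan, and a 6.5 cm tumour needs 1.5 cm. Baseline size is therefore prognostic almost by construction.

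Randomisation is not stratified on size or lesion number, and the analysis does not adjust for them. A chance imbalance in this mix can then pass into the estimated arm difference. Downstaging is one of two secondary endpoints, is read in only part of the 220 patients and has no power statement of its own. Precision available from data already held is worth having there.

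**Working it through.** **The plan's own figure.** None exists for downstaging. The 110 per group with 80% power concerns mortality and has no bearing here. Subset size, SDs, baseline-to-post correlation and shrinkage below are assumptions.

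**1. Distance to Milan (Appendix 1).** Solitary: 6.5 - 5 = 1.5 cm at most. Multiple (Milan: "3 lesions, none of" more than 3 cm): 4.5 - 3 = 1.5 cm at most for the largest lesion. Both start just above 0.

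**2. Baseline spread.** Assume half solitary, with sizes uniform within the allowed ranges.
- Within-group variance: 1.5²/12 = 0.1875. Between-group variance, with means 5.75 and 3.75: 1² = 1.
- SD = √1.1875 = 1.09 cm.
- SE of the chance baseline difference at 35 per arm: 1.09 × √(2/35) = 0.26 cm, a 95% range of about ±0.5 cm. That is a third of the largest fall required.

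**3. Diameter outcome, no complete responses.** Simulation of 1,500 trials per setting, with lognormal shrinkage (SD 0.35). At 30 per arm the SE of the arm difference is 0.384 cm (t-test on post-treatment diameter), 0.331 (t-test on change) and 0.326 (ANCOVA).
- Variance cut against post-treatment: 1 - (0.326/0.384)² = 28%.
- Variance cut against change: 1 - (0.326/0.331)² = 3%.

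| Per arm | Power, post | Power, change | Power, ANCOVA |
|---|---|---|---|
| 30 | 40% | 51% | 53% |
| 40 | 52% | 65% | 68% |

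Repeat simulations under similar assumptions gave about 25-27% against post-treatment diameter and 0-2% against change.

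**4. Why the comparator matters.** With equal baseline and post-treatment SDs, the ANCOVA variance ratio is 1 - ρ² against post-treatment and (1 + ρ)/2 against change. At ρ = 0.5 both are 0.75, a 25% cut against either. The equal-SD premise does not fit step 3: 0.384/√(2/30) = 1.49 cm post-treatment, against 1.09 cm at baseline. With those SDs and ρ = 0.54 (from a re-run of the same set-up):
- ANCOVA: 1.49² × (1 - 0.54²) = 1.573.
- Change: 1.49² + 1.09² - 2 × 0.54 × 1.49 × 1.09 = 1.654.
- Ratio 0.951, a cut of about 5% before the small cost of estimating extra terms. This is in line with the simulated 3%.

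**5. Sensitivity to the shrinkage model.** With proportional normal shrinkage at 22, 33 or 55 per arm (ρ from 0.51 to 0.80), ANCOVA gained about 7 to 37 power points over post-treatment diameter and -0.4 to +2.3 over change.

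**6. Milan reached yes/no.** In the step 5 simulation, excess over the applicable limit plus solitary/multiple explained 4-16% of outcome variance. Covariate-adjusted linear regression with robust errors moved power by -1 to +5 points against chi-squared (for example 44% to 47% at 22 per arm, 63% to 63% at 33, 81% to 86% at 55). Raw diameter alone explained about 0%, because a 4.4 cm lesion in multiple disease must fall 1.4 cm and a 5.1 cm solitary one 0.1 cm. Excess equals diameter minus 5 (solitary) or minus 3 (multiple), so diameter plus solitary/multiple is the same model as excess plus solitary/multiple.

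**7. Complete responses.** The measure is viable diameter, which is zero once arterial enhancement has gone. Re-run of step 3 at 30 per arm (mean log shrinkage -0.25, arm effect -0.2, random zeros in both arms):

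| Zeros | Power, post | Power, change | Power, ANCOVA |
|---|---|---|---|
| 0% | 43% | 54% | 55% |
| 30% | 14% | 16% | 15% |
| 60% | 9% | 8% | 9% |

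At 30% zeros the correlation falls from 0.54 to 0.27, and the variance cut is about 3-4% against either t-test.

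**The case against.** The strongest reply is that the Downstaging section describes a pre-and-post comparison. With a t-test, the natural reading is change from baseline, which already uses baseline by subtraction. A reader might infer from the bare list of tests that the plan disregards baseline tumour size altogether; the documents do not support that. They leave the scale open. A post-treatment diameter or a yes/no outcome would leave baseline out, and a change score would not.

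A reader might also take 25-28% as the precision lost. That figure belongs only to a t-test on post-treatment diameter, which the plan does not specify. Against a change score almost nothing is gained, and with no complete responses a t-test on percent change did as well as ANCOVA (58% against 55% power at 30 per arm). Complete responses shrink the gain further, and the Proton Beam Radiotherapy background cites complete tumour disappearance in 80% of one series.

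Nor is this a bias or a type I error problem: randomisation protects the unadjusted test, whose error rate already allows for chance imbalance. Longest diameter also sets the distance to Milan only in part. Two 4 cm lesions fit San Francisco (total 8 cm), and both must fall to 3 cm.

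All of this stands and limits the size of the point. It does not remove it. Under 1:1 randomisation ANCOVA is, in large samples, no less precise than a t-test on either post-treatment diameter or change, and in these simulations it was essentially never worse. Naming it in advance removes the dependence on a choice the plan has not made.

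**Conclusion.** The point holds as a free improvement, not as an error. The plan specifies no baseline adjustment for downstaging, although the covariates are already in hand. The cost is some precision and exposure to chance imbalance, without bias.

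With 30 to 40 per arm, half solitary and no complete responses, the variance reduction is roughly 25-28% if the plan means post-treatment diameter and about 0-3% if it means change. For yes/no the effect on power is about -1 to +5 points. With 30-60% zero diameters the power gain is about nil. These figures rest on an assumed subset size, lesion mix and shrinkage distribution, and the simulations follow only the largest lesion. The documents supply none of these inputs, so calling the subset small is plausible but not established.

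The undefined outcome scale and time point come first, since no adjusted model can be written until they are settled.

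**What to change.** 1. **Define the outcome.** State whether downstaging is viable diameter or Milan reached yes/no, at which already planned scan it is read, and how loss of all enhancement is scored. Follow Up (4-6 weeks after treatment) and Appendix 3 (six to 12 weeks after TACE) describe the first scan differently and must be reconciled.
2. **If a diameter:** make the primary between-arm analysis ANCOVA of post-treatment viable diameter on arm, baseline viable diameter and solitary/multiple.
3. **If yes/no:** report a risk difference standardised from a logistic model on arm with the same baseline terms, or equivalently excess over the applicable Milan limit plus solitary/multiple. Do not use raw diameter alone.
4. **Keep the unadjusted test** as supportive.

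Cost: a short SAP paragraph, once the outcome definition has been agreed. No new measurement, visit or patient is needed. Fixing scale and model beforehand also prevents a later choice among post-treatment, change and yes/no results.

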### **San Francisco Criteria**

Solitary lesion  $\leq$  6.5 cm or  $\leq$  3 lesions none  $>$  4.5 cm and total tumor diameter  $\leq$  8 cm

## Appendix 2

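### Downstaging is never defined as reaching Milan criteria, and change in the one measure named, the longest viable diameter, does not determine Milan status

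*Combined protocol and SAP*

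**What the plan says.** Under Secondary Endpoints, 2. Downstaging, the population is clear: "This endpoint will be applied to subjects in whom their tumor burden exceed Milan criteria but meet San Francisco criteria (Appendix 1"). So is the purpose. The section explains that these patients do not get a MELD exception "unless their tumor burden is down-staged to Milan criteria using one of the locoregional treatments", and that the endpoint is there to compare the two treatments on this. The one measurement given is: "The direct measurement of the longest diameter of the viable tumor will be compared pre-and-post treatment".

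Appendix 1 defines both sets of criteria by lesion number as well as size. Milan allows one lesion up to 5 cm, or up to three lesions with none above 3 cm. San Francisco allows one lesion up to 6.5 cm, or up to three with none above 4.5 cm and a total of at most 8 cm.

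Data and Statistics states: "Secondary end points will be compared using Student's *t*-test for quantitative data", with chi-squared or Fisher's exact test for qualitative data. It does not say which type downstaging is.

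On timing, Methods gives TACE as one or more sessions and proton as 15 consecutive sessions. Follow Up describes imaging 4-6 weeks after treatment and every three months after that, and says that no imaging will be ordered for the study. Appendix 3 mentions repeat imaging six to 12 weeks after TACE.

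**The concern.** The question is about a threshold: is the patient now within Milan or not? The measurement offered is a continuous one taken before and after treatment. A diameter is quantitative, so a reader following Data and Statistics would most naturally compare the change in diameter between arms by t-test. That analysis says which treatment shrinks the largest viable lesion more. It does not say what proportion of patients were downstaged, which is the figure that bears on transplant eligibility.

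Three items needed to produce that proportion are missing: a definition of success, the number of viable lesions after treatment, and the scan at which status is judged. Leaving them open also leaves the choice between two different analyses until the data are in hand.

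**Working it through.** The documents give no rate, sample size or power for downstaging, so there is no figure to reproduce. The check is whether change in the longest viable diameter determines Milan status under Appendix 1.

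**1. Patients ranked the wrong way round.** Every baseline below is beyond Milan and within San Francisco criteria. Change = (after - before) / before, for the longest lesion.

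| Baseline (cm) | After (cm) | Change in longest diameter | Milan status after |
|---|---|---|---|
| solitary 6.5 | 5.1 | -1.4/6.5 = -21.5% | outside (5.1 > 5) |
| solitary 5.2 | 4.9 | -0.3/5.2 = -5.8% | within |
| 4.0 + 3.5 (total 7.5) | 3.2 + 2.8 | -0.8/4.0 = -20.0% | outside (3.2 > 3) |
| 3.2 + 3.0 (total 6.2) | 2.9 + 2.8 | -0.3/3.2 = -9.4% | within |

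In each pair the patient with the larger shrinkage is the one not downstaged.

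**2. Same change, different status.** The longest diameter falls by 1.0 cm in all three cases:
- solitary 5.5 to 4.5 cm: within Milan;
- 4.5 + 2.0 to 3.5 + 2.0 cm: outside, because two lesions are present and 3.5 > 3;
- solitary 5.5 to 4.5 cm with a new 2.0 cm lesion: outside, because two lesions are present and 4.5 > 3.

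**3. Shrinkage needed to reach Milan.** For a solitary lesion of d cm it is 1 - 5/d. For multiple lesions with longest d cm it is 1 - 3/d.
- Solitary: 5.1 cm needs 2.0%, 5.5 cm 9.1%, 6.0 cm 16.7%, 6.5 cm 23.1%.
- Multiple: 3.1 cm needs 3.2%, 3.5 cm 14.3%, 4.0 cm 25.0%, 4.5 cm 33.3%.

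No single percentage change therefore corresponds to downstaging.

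**4. How often ranking fails (illustration; all inputs assumed).** Baseline sizes were drawn uniformly: 5.01 to 6.5 cm if solitary, otherwise two or three lesions of 1 to 4.5 cm each. Only sets beyond Milan and within San Francisco were kept. Each lesion shrank independently by a mean of 15% or 30% (SD 20%), with no new lesions. The solitary share ran from 1% to 100%. Take pairs of one downstaged and one not downstaged patient. The share in which the downstaged patient shrank less was:
- about 3.5% to 10% by absolute change;
- about 2.5% to 7% by percent change.

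Ranking by the post-treatment longest diameter without a lesion count failed in 0% (all solitary) to 22.5% of pairs (30% solitary, mean shrinkage 15%). The lower limit of 1 cm in multifocal sets is looser than the exclusion of lesions below 2 cm, so these shares indicate scale only.

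**The case against.** The best defence is that the intent is plain. The endpoint is called Downstaging, is confined to patients beyond Milan, and is explained by reference to Milan. On that view the diameter is simply the measurement from which Milan status is read, and chi-squared or Fisher is already available for a yes/no result. Much of this stands. A reader might infer that the plan has committed itself to a t-test on mean diameter change, but the documents do not support that: the Downstaging section names no test and no mean change, and Data and Statistics does not classify the endpoint.

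It is also true that the measurement is usable. For a patient who stays solitary, the post-treatment diameter alone settles Milan status. For multifocal patients without new lesions it settles the 3 cm limit, since entry is capped at three lesions. The section on time to progression already provides two independent radiologists and a rule for when a new nodule counts as HCC. The data will exist.

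The defence does not supply the rule. Nothing states that the outcome is Milan status, that viable lesions are counted for it, or when it is judged. The simulation suggests that diameter change and Milan status usually agree, but agreement in most pairs is not a definition.

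**Conclusion.** The concern holds in a limited form. The plan names one measure for downstaging, and change in that measure does not determine whether Milan was reached. This follows from Appendix 1 alone and needs no assumption. Patient-level misranking is real. Its frequency (a minority of pairs, about 2.5% to 10% by change in diameter) rests entirely on assumed sizes and shrinkage. That the endpoint would fail to answer its own question depends on its being analysed as a quantitative change.

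Three stronger inferences should not be drawn:
- **One arm could win on shrinkage while converting fewer patients.** The examples compare individuals, and the simulation has no treatment arms. An arm-level reversal has not been shown.
- **The open assessment time favours a particular arm.** That would need a rule such as best response over all scans, and none is stated. What is open is which scan counts and, for repeated TACE, which session starts the clock. The direction of any bias is unknown.
- **Patients who die or have no scan are dropped.** The plan states intent to treat and expects no significant drop-out. How such patients are handled for this endpoint is unspecified, which is different from excluding them.

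This is a secondary endpoint in a subgroup whose expected size the plan does not give. It should be corrected, but it does not touch the primary endpoint or the 110 patients per group.

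**What to change.** Define downstaging as yes/no: viable tumour burden within Milan, judged on the number of viable lesions and the largest viable diameter by the two-radiologist reading.

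- **Time:** the routine scan falling in one prespecified window, the same in both arms, with its starting point stated. Because no imaging is ordered for the study and routine scans are tied to treatment, the window must be matched to the Follow Up schedule and wide enough to hold a routine scan in both arms. The scan timings in Follow Up and Appendix 3 should be reconciled first.
- **Denominator:** all randomized patients beyond Milan but within San Francisco criteria at baseline.
- **Other outcomes:** death before the window, or no scan in it, counts as not downstaged. State in advance how transplant before the window is classified, since follow-up ends at transplant.
- **Analysis:** compare proportions with the planned chi-squared or Fisher test, and report change in longest diameter descriptively.

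The cost is an amended endpoint definition and analysis text, with no new scans or measurements. The price in information is that a yes/no outcome is less sensitive than a continuous one, in what is already a subgroup. Counting a missing scan as failure is a convention, and the plan should say so.
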